We will enroll menthol (n = 125) and non-menthol (n = 125) YA smokers who initiated regular smoking in the past 12-months or who initiated regular smoking more than 12 months ago, and measure appeal/reinforcement for menthol and non-menthol cigarettes and the impact of appeal/reinforcement on changes in smoking (progression, nicotine dependence, and cigarette harm perceptions) at a 6-month follow-up. Appeal/reinforcement will be assessed via two complementary measurement paradigms: one in the laboratory using a well-validated behavioral economic choice task and the other in the natural environment using ecological momentary assessment (EMA). Laboratory studies provide a great deal of efficiency and internal control, allowing for causal inference of acute subjective response; while EMA allows for similar causal sequencing of behavior, but in an ecologically valid format in the smoker's natural environment. It is hypothesized that, compared to nonmenthol smokers, menthol smokers will show greater appeal/reinforcement, both in the laboratory and via EMA, and will be more likely to show progression to regular smoking, increases in nicotine dependence, and lower cigarette harm perceptions by a 6-month follow-up. The association between menthol preference and smoking outcomes will be reduced or non-significant after including measures of appeal/reinforcement in the model; suggesting that menthol's appeal/reinforcement accounts for smoking progression. This research will isolate the unique effects of menthol in smoking and will help inform regulatory decisions about the abuse liability of menthol cigarettes and the use of flavors in other tobacco products in future studies.

Specific Aims

Aim 1 (Phase 1): Examine the absolute and relative reinforcing value (appeal) of menthol vs. non-menthol cigarettes using a validated laboratory-based behavioral economic choice task.

Aim 2 (Phase 2): Examine the subjective effects (appeal) of menthol vs. non-menthol cigarettes (own brand) during 14 days of ecological momentary assessment (EMA) in the natural environment.

Aim 3 (Phase 3): Examine the degree to which laboratory (Phase 1) and EMA (Phase 2) measurements of menthol appeal/appeal causally impact (i.e., mediate) the association between menthol brand preference at baseline and 6-month smoking outcomes (progression, increased nicotine dependence, lower cigarette harm perceptions).

Study Design

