Participants will be asked and reminded not to send PHI via email or any other unapproved system. Research data will only be collected and recorded via approved data collection systems (e.g. REDCap and mHealth Insight)

Laboratory Visit /Session 1: Baseline Assessment and Ad Libitum Smoking. Visit 1 (between-subjects) will measure absolute reinforcing value (ARV) of menthol vs non-menthol cigarettes via a 60-minute ad libitum smoking session of one's usual cigarette type (menthol or non-menthol). Subjective response (e.g., smoking satisfaction, craving reduction, psychological reward, sensory effects like throat hit), smoking exposure (CO boost), and behavior (topography: number of puffs, total time smoked) will be measured.

After completing the initial screening over the phone, participants will be informed of the study procedures and invited to the lab to complete the three laboratory visits (If in-person data collection is occurring and if they choose to come to the laboratory). During scheduling for Visit 1/Session 1, they will be reminded to bring at least two of their cigarettes to the first study visit and will be asked to abstain from nicotine and tobacco products, and any other combustible product (e.g., cannabis) for at least 12 hours prior to each study visit. If they are going to attend an in-person session, they will be reminded to wear a mask and that they will be asked about any changes in the COVID-19 screener since they were first asked. If an individual selects virtual study sessions, they will be asked to complete the visit 1 procedures remotely using a remote topography device and iCO carbon monoxide reader to confirm smoking recency. In-person participants will provide a breath sample to measure carbon monoxide levels and asked when the last time they smoked a cigarette was. We will use password protected video conferencing to allow study staff to assist participants and complete this and the below procedures.

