Phase 3 will examine the degree to which laboratory and EMA measurements of menthol appeal causally impact (i.e., mediate) the association between menthol brand preference at baseline to 6-month smoking outcomes. Participants will complete a follow-up survey that will be scheduled to occur 6 months after they are enrolled in the study to assess cigarette smoking (frequency and intensity in the past 30-days), nicotine dependence, absolute smoking harm perceptions ("How harmful are cigarettes to your health?"), and relative smoking harm perceptions ("Compared to non-menthol cigarettes, how harmful to your health are menthol cigarettes?"). Follow-up assessment can be completed either in-person, or via telephone or web-assessment (if in-person follow-up is not viable). Participants will also be asked to complete two interim assessments (2-months and 4-months post enrollment) to enhance retention rates through the 6-month follow-up. These surveys will be brief and query about tobacco use behavior in the past 30-days. Participants will be given a reminder notification approximately two-weeks before their scheduled follow-up assessment (timeframe may be a few days longer or shorter due to holidays). All other baseline variables will be re-assessed at the follow-up, in addition to questions about cessation attempts and new tobacco product initiation, including flavored tobacco use (where applicable). We will use several strategies to encourage completion of the study by providing participants: 1) a calendar of their appointments throughout the study; 2) reminder calls the day prior to a scheduled visit; 3) monetary incentives at each visit; and 4) a completion bonus.

Participants

Participants will be $n = 125$ menthol and $n = 125$ non-menthol young adult (YAs) who started smoking regularly in the past 12-months or initiated regular smoking more than 12 months ago.

Participant Recruitment

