In addition to the aforementioned recruitment methods, we will use BuildClinical, who will assist with recruitment by designing and managing targeted, GCP-compliant, IRB approved advertising. **BuildClinical** is a data-driven software platform that helps academic researchers recruit participants for research studies more efficiently using social media, software, and machine learning. BuildClinical utilizes study-specific advertisements to engage participants on digital platforms such as Facebook, Google, WebMD, etc., and redirect them to a study-specific landing page should they click it. On the landing page, the person can complete an online pre-screen questionnaire that gets routed into BuildClinical's platform. BuildClinical's Secure Socket Layer (SSL) software, which encrypts all inputted information, keeps participant information private and HIPAA compliant. BuildClinical's backend servers are stored in the USA at some of the most secure data centers in the world. The study team will access BuildClinical's platform to review and select qualified screening participants for additional screening. Interested individuals may then choose to enroll in the study by completing Informed Consent and HIPPA prior to scheduling a baseline lab or virtual session.

We have included the BuildClinical advertisement materials, pre-screening questionnaire, and study information landing page design and

IRB NUMBER: 10581
B NUMBER: 10581
IRB APPROVAL DATE: 02/14/2022
PROVAL DATE: 09/13/202112

content.[Inclusion/Exclusion criteria](#)

Inclusion criteria:

- (1) Ages 18 to 26;
- (2) Currently smoke cigarettes "somedays" or "everyday";
- (3) Started smoking "somedays" or "everyday" in the past 12-months or more than 12 months ago.
- (4) A strong preference for menthol or non-menthol cigarettes (i.e., smoke one type $\geq 80\%$ of the time).
- (5) Able to read and understand the informed consent
- (6) Willingness to abstain from nicotine containing products or other combustible products (e.g., smoked cannabis) for at least 12 hours prior to each in-person or virtual laboratory visit (confirmed by CO $\leq 8\text{ppm}$ for each in-person study visit in Phase 1). Will be rescheduled once if CO is not within acceptable range.

Exclusion criteria:

- (1) Current use of nicotine replacement therapy (NRT);
- (2) Currently pregnant or planning to become pregnant, or breast feeding (verified by pregnancy test at each study visit/session);

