The main outcome analyses for Aim 3 will examine the predictive validity of laboratory (Phase 1) and EMA (Phase 2) outcomes on changes in the 6-month outcomes of interest, and the degree to which laboratory and EMA ratings of appeal/reinforcement account for (i.e., mediate) the association between menthol brand preference at baseline and smoking behavior change. Hierarchical regression models (continuous or binary logistic) will predict the 6-month outcome of interest, controlling for baseline levels of the outcome in interest and relevant demographics (gender, race/ethnicity, age of smoking onset) in Step 1, baseline menthol status in Step 2, and then laboratory or EMA-derived slopes Step 3. Models will be conducted separately using Phase 1 and Phase 2 measurements of appeal/reinforcement. Mediation will be reflected by a reduction in the association between baseline menthol preference and smoking outcomes after including the requisite measure of appeal/reinforcement in the model. Covariates with $p < .05$ will be retained in final models.

Exploratory analyses will examine changes over time in tobacco use behavior from baseline, 2,4, and 6-months. All data collected during the course of the study, survey and bio-specimen results, will be maintained for future use in cross-reference against new and continued data collection.

Human Subjects Protection

Potential Risks

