This is a low-risk observational study and we do not anticipate any Serious Adverse Events. Because a Data and Safety Monitoring Board is only required for higher risk and/or multisite studies, and the proposed research is a single site study with minimal risk, a formal Data and Safety Monitoring Board formed is not required. We do, however, have a detailed data and safety monitoring plan. Adverse events will be assessed by research personnel at each study visit via participant self-report and managed immediately. All serious adverse events will be reported to the OUHSC IRB.

We will monitor for risk of using cigarettes by screening participants via self-report for general medical precautions (pregnancy, cardiovascular disease). The most likely adverse event (potential for nicotine overdose) is anticipated to be rare (< 1%) and mild (nausea, headache) and will be handled quickly (i.e., advice to participant to reduce or eliminate cigarette use). The PI will be available for any questions that participants may have about smoking, or smoking cessation. Participants will be given contact numbers of the laboratory and PI. Any adverse events, breaks of confidentiality, or any other data or safety issues that arise will be discussed immediately with the PI ([name]). [name], or a delegate (Project Manager) will be responsible for completing an Adverse Events Form should an event occur. The Adverse Events Form will be reviewed by the PI and will report Serious Adverse Events to the OUHSC IRB within 24 hours of having received notice of the event. [name] will gather any information needed to investigate the event and to determine subsequent action. Any subsequent action will be documented and reported to the OUHSC IRB.

Potential benefits of the proposed research to participants

The participants may benefit directly through increased understanding of factors underlying uptake, appeal, and use of menthol cigarettes, which is linked to smoking progression and poor cessation outcomes. This study is designed to answer important questions about factors that promote tobacco use behavior with the ultimate goal of informing prevention and regulatory decisions about menthol cigarettes and other flavored tobacco products. Improved regulation could ultimately help deter tobacco use among the larger population of young people, thus decreasing overall rates of tobacco-related morbidity and mortality, including those that stem from tobacco use and dependence.

References

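### Aim 3 claims that appeal causally mediates menthol preference and 6-month smoking, but liking that existed before the choice of menthol could give the same coefficient drop, so direction is not identified

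*Combined protocol and SAP*

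**What the plan says.** Specific Aims, Aim 3, sets out to examine how far the laboratory and EMA measures of "menthol appeal/appeal causally impact (i.e., mediate) the association between menthol brand preference at baseline and 6-month smoking outcomes". Phase 3 Overview and Experimental Design repeats the causal claim: "laboratory and EMA measurements of menthol appeal causally impact (i.e., mediate) the association".

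The Study Objective and the opening summary add the intended reading. If the menthol association shrinks or loses significance once appeal is in the model, this is taken to suggest that menthol's appeal explains smoking progression. Both also say the work will inform regulatory decisions.

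The analysis is in Data Analysis Plan, Phase 3/Aim 3 Analyses. Step 1 enters the baseline level of the outcome, gender, race/ethnicity and age of smoking onset. Step 2 enters baseline menthol status. Step 3 enters the laboratory measures or the EMA-derived slopes. The criterion is: "Mediation will be reflected by a reduction in the association between baseline menthol preference and smoking outcomes" once the appeal measure is included.

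The exposure is not assigned. The inclusion criteria require "A strong preference for menthol or non-menthol cigarettes", defined as smoking one type at least 80% of the time. The first appeal measure comes after enrolment, from a "60-minute ad libitum smoking session of one's usual cigarette type (menthol or non-menthol") at Visit 1. The Visit 3 breakpoint and the slopes from 14 days of EMA are also collected after enrolment.

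**The concern.** A fall in the preference coefficient shows mediation only if preference influences appeal and nothing unmeasured drives both preference and smoking. Participants chose their cigarette type before anyone measured how much they liked it. Liking may have led some of them to menthol and may also go with heavier smoking. In that case appeal is a common cause of preference and smoking, not a step between them, and adding it to the model still removes the preference coefficient.

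The kind of liking that matters depends on the mediator. For the Visit 1 ratings of the usual cigarette, general enjoyment of smoking is enough. For the Visit 3 choice task and the EMA slopes, which contrast menthol with non-menthol, it would have to be liking specific to menthol.

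At stake is the conclusion. A positive Aim 3 result would go to regulators as a causal mechanism, although the same result could arise with menthol use having no effect on 6-month smoking.

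**Working it through.** The plan gives no effect size, power or expected coefficient for Aim 3, so there is no figure to reproduce. The check asks whether the Step 2 and Step 3 regressions can tell two causal orders apart.

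**Inputs from the plan.** 125 menthol plus 125 non-menthol smokers gives n = 250. Adjustment is for the baseline outcome; demographics were not simulated. The criterion is the change in the menthol coefficient from Step 2 to Step 3.

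**Assumed inputs, with ranges.** Preference–appeal effect a = 0.3, 0.5, 0.8; appeal–outcome effect b = 0, 0.2, 0.4; reliability of measured appeal 1.0 or 0.7.

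**Two worlds.** X is menthol preference, A appeal, Y0 and Y6 the baseline and 6-month outcomes.
- World 1, menthol raises appeal: X ~ Bernoulli(0.5), A = aX + N(0,1).
- World 2, appeal drives choice and menthol does nothing: A has the same marginal distribution as in World 1, and P(X=1|A) = 1/(1 + exp(−(aA − a²/2))).
- Both: Y0 = 0.3A + N(0,1); Y6 = 0.5·Y0 + bA + N(0,1).

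The log ratio of the N(a,1) and N(0,1) densities at A is aA − a²/2. World 2 is therefore the exact Bayes inverse of World 1, and X, A, Y0 and Y6 have the same joint distribution in both.

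**Closed form, valid in both worlds.** The X coefficient in the regression of A on X and Y0 is a/(1 + 0.3²).
- Step 2 = ab/(1 + 0.3²). At a = 0.5, b = 0.4: 0.20/1.09 = 0.1835.
- Step 3 with perfectly measured appeal = 0.
- Step 3 at reliability 0.7: Var(A) = 1 + 0.5²/4 = 1.0625; error variance v = (1/0.7 − 1) × 1.0625 = 0.455; coefficient = ab/(1.09 + 1/v) = 0.20/(1.09 + 2.196) = 0.0609.
- Drop at reliability 0.7 = 0.1835 − 0.0609 = 0.1226, or 67% of the Step 2 coefficient.

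**Simulation at n = 250, 2,000 runs per setting** (drops computed before rounding). The true total effect of menthol in World 1 is a(b + 0.5 × 0.3); in World 2 it is 0.

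| a | b | Reliability | World 1, Step 2 → 3 | World 2, Step 2 → 3 | Drop, World 1 / 2 | True effect, World 1 / 2 |
|---|---|---|---|---|---|---|
| 0.3 | 0.2 | 1.0 | 0.056 → 0.001 | 0.051 → −0.005 | 0.055 / 0.056 | 0.105 / 0 |
| 0.5 | 0.4 | 1.0 | 0.186 → 0.003 | 0.181 → −0.003 | 0.183 / 0.185 | 0.275 / 0 |
| 0.5 | 0.4 | 0.7 | 0.179 → 0.055 | 0.183 → 0.059 | 0.124 / 0.123 | 0.275 / 0 |
| 0.8 | 0.4 | 1.0 | 0.296 → 0.002 | 0.294 → −0.001 | 0.295 / 0.295 | 0.440 / 0 |
| 0.5 | 0 | 1.0 | −0.002 → −0.001 | 0.006 → 0.007 | −0.001 / 0.000 | 0.075 / 0 |

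Significance rates match too. At a = 0.8, b = 0.4, reliability 1.0, Step 2 is significant in 58% and 57% of runs, and Step 3 in 6% and 5%.

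**Contrast-type mediators.** A separate large-sample run had menthol do nothing to smoking and, for simplicity, no baseline outcome. Assumed inputs were a choice logit slope of 0.5 and a smoking slope of 0.3. If general liking drives choice and smoking, a menthol-minus-non-menthol contrast leaves the coefficient at about 0.14 before and after. If menthol-specific liking drives both, the coefficient goes from 0.143 to 0.002.

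**The case against.** Four points on the other side deserve weight.

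**Order of measurement.** A reader might infer that measuring appeal after preference is itself the flaw. It is not: a mediator should follow the exposure, and the order from appeal to 6-month outcome is sound. What is missing is any account of liking from before the choice.

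**Within-person evidence.** A reader might also infer that nothing in the plan bears on whether menthol raises appeal. That goes too far. At Visit 2 each participant samples menthol and non-menthol versions of the same cigarette in counterbalanced order, which tests menthol's acute effect on appeal directly. The Visit 3 task and the EMA slopes are also menthol-versus-non-menthol contrasts, and general liking does not produce a drop for those. This stands and narrows the point. But the Phase 1/Aim 1 Analyses section makes the experimental-cigarette ratings only a potential covariate for Aim 3. Menthol-specific liking that preceded the choice still reproduces the drop for the contrast measures.

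**Baseline adjustment.** Step 1 controls for the baseline outcome, which shrinks the coefficient. It does so equally in both worlds.

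**Existing hedges.** The analysis section also uses softer wording about accounting for the association, and the hypothesis is worded as suggestive. The aim and the Phase 3 overview nevertheless say causally. The statement "This is a low-risk observational study" adds little, since it appears in the explanation of why no safety board is needed. The entry criterion is what shows that preference is not assigned.

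**Conclusion.** The point holds. The coefficient drop that Aim 3 treats as mediation is equally compatible with pre-choice liking driving both preference and smoking, and the design does not identify which. At a = 0.5 and b = 0.4 the drop is about 0.18 in both worlds with perfect measurement and about 0.12 in both at reliability 0.7, while menthol's true effect on the 6-month outcome is 0.275 in one world and 0 in the other.

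The sizes rest on assumed effects; the equality does not, because the joint distributions are identical. A larger sample or a formal test of the indirect effect on these variables would therefore not resolve direction. The result needs appeal to matter beyond the baseline outcome; at b = 0 there is no drop to interpret. For the choice task and EMA slopes it also needs menthol-specific liking to be linked to later smoking.

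Two stronger conclusions are not supported. The documents do not imply that menthol has no effect on appeal, since Visit 2 can test that. Nor should complete removal of the coefficient be expected: that requires perfectly measured appeal, and at reliability 0.7 about two thirds is removed.

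**What to change.** - **Specific Aims (Aim 3) and Phase 3 Overview:** replace the causal-mediation phrase with *statistically account for*.
- **Opening summary and Study Objective:** qualify the planned inference to say that a reduced association would be explained statistically by appeal, and that the direction between preference and appeal is not identified.
- **Phase 3/Aim 3 Analyses:** report the Step 2 to Step 3 change as association explained. Alternatively, keep the term mediation, state the no-confounding and direction assumptions, and add a sensitivity analysis for liking that preceded the choice.

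None of this needs new participants, visits or measures. The wording route costs a more modest claim; the alternative adds one sensitivity analysis.

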to start time). The participant will attend an initial baseline visit, where informed consent will be completed and a baseline experimental visit of ad libitum smoking of one's preferred cigarette brand, and two additional visits later. The \geq 12-hour abstinence requirement was chosen because it controls for recent smoking exposure and produces optimal levels of smoking motivation that are sensitive to the experimental manipulations⁷ including the paradigm used in the current proposal, and prevents greater attrition and non-compliance relative to more prolonged periods.¹⁵⁷ Participants will be compensated \$45 for each in-person laboratory smoking visit in which they are eligible, or \$25 for Visit 1 if they are deemed ineligible. Participants will also be compensated \$35 for completing the baseline survey. Individuals will be compensated \$10 for each in-person visit (up to \$30).

Following are the standard procedures that have been adopted for the HPRC and OUM/OUHSC for all studies that will be facilitated in-person and would be utilized for this study in response to COVID-19.

PROCEDURE:

1. Employees will comply with all OUHSC COVID related policies and procedures as currently exist and as are revised in the future.
2. Efforts will be made to minimize face-to-face time with participants. When possible, consents will be sent to participants at their homes and reviewed by phone or zoom, as available. Additional items, including pregnancy tests, will also be shipped to the home, and reviewed over phone or zoom, when possible.
3. During scheduling, participants will be asked to wear a mask, if they have one available, to their appointments. For participants who do not have access to a face mask, they will be told that one will be provided. They will also be asked the questions from the OUM/OUHSC COVID19 Questionnaire (see attached in "Other Documents"). If the patient is symptomatic or has known direct contact with a person with COVID-19 they will be asked to consult with their PCP prior to re-scheduling their visit.
4. Participants will be instructed to call from their vehicle upon arrival for their appointment to prevent participants from congregating in the waiting room. They will also be verbally asked if any of their answers from the COVID-19 questionnaire have changed since their original completion. If the patient is symptomatic or has known direct contact with a person with COVID-19 they will be asked to reschedule their appointment.

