After completing questionnaires, ARV will be measured by having participants smoke their usual brand of cigarette (*ad libitum*), which they will be instructed to bring with them to the first study visit. They will smoke through a mouthpiece of the Cress Smoking Topography Device, during a 60-minute smoking Visit or the SODIM Smoking Puff Analyzer Mobile SPA-M The CReSS or SODIM instrument will record puff volume, duration and velocity and inter-puff interval for each puff and their aggregate averages.⁷⁻¹⁰ Puff topography measures will be used to examine whether increased puff volume, duration, and lower inter-puff interval differ across menthol and non-menthol cigarettes. Before and after smoking, heart rate and blood pressure will be collected (if session is taken in person); exhaled carbon monoxide (CO boost), and subjective response to smoking (craving reduction, psychological reward, satisfaction, sensory effects) using the Cigarette Evaluation Questionnaire (CEQ). Exhaled carbon monoxide will be collected and measured in ppm immediately before and after smoking. At the completion of Visit 1, participants will be paid for the visit, and scheduled for study visits (V2 and V3).

Laboratory Visit or Session 2: Sampling Experimental Cigarettes and Cross-Price Elasticity Task. Participants will confirm abstinence by being asked the last time they smoked a cigarette in addition to providing a carbon monoxide measurement (CO \leq 8 ppm). Visit/Session 2 (within-subjects) will familiarize participants with the experimental cigarette (Camel Crush) by having them take a minimum of 3 and up to 5 puffs each of a menthol and non-menthol version (counterbalanced) and complete subjective ratings,

smoking exposure (CO boost), and behavior (topography: total time smoked). There will be a 20 minute washout period between each cigarette smoked, per our consultant's ([name]) paradigm protocol¹¹⁻¹⁴. Before and after smoking heart rate and blood pressure will be recorded (if session is taken in person), approximately 5 minutes after smoking subjective response, and CO boost will be recorded. After another 20 minute wait period from the last cigarette puff.

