Primary Outcomes: **(a)** the absolute reinforcing value (ARV) of menthol cigarettes from Visit 1, **(b)** the relative reinforcing value (RRV) of menthol cigarettes from Visit/Session 3 based on Choice Task responding; **(c)** RRV of own vs experimental brand based on price elasticity. ARV of menthol cigarettes will be operationalized as between subject differences in subjective ratings of menthol vs non-menthol cigarettes (satisfaction, reward, craving reduction, physical sensations) during the ad libitum smoking Visit. RRV will be measured by evaluating motivation to “work harder” for menthol versus non-menthol cigarette puffs or for one’s own brand from Visit 3. This is operationalized by the highest trial (breakpoint) that a participant successfully works for a menthol vs nonmenthol cigarette puff (or for their own vs experimental brand). Higher values reflect greater RRV of menthol cigarettes relative to non-menthol cigarettes (or their own brand vs the experimental brand. RRV of own vs experimental brand will be operationalized as cross-price elasticity of demand which measures the responsiveness of the quantity of experimental cigarettes that are self-reported to changing prices of the preferred cigarette brand.

Secondary Outcomes: **(a)** Total number of responses for the menthol versus the non-menthol-cigarette on the choice task **(b)** CO boost; and **(c)** puff topography (number of menthol versus non-menthol cigarette puffs consumed, number of minutes smoked, interval between puffs). Exploratory analyses will compare ARV and RRV.

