Risk of smoking cigarettes. The risk of side effects and adverse events are moderate to low. The cigarettes smoked during the course of this study will be either the participant's own brand provided by the participant, or a Camel Crush cigarettes. These products are sold online and at convenience and specialty stores nationwide. Although smoking is associated with disease, we do not expect the disease risk to be significantly greater from smoking the study cigarette. Participants will be told that they have the right to drop out of the study at any time and will be paid for what they have completed up to that point. They will also be informed that smoking is dangerous for one's health, but that the smoking involved in the study poses no more harm than their usual smoking exposure. At the end of the study, or upon request, participants will be given a list of resources to assist them to quit smoking should they be interested.

All participants will be: 1) screened for general medical precautions (pregnancy via urine dip stick test for females, asking for history of CF, COPD, asthma, and heart or lung disease) and 2) monitored for adverse events during the study period. Study personnel will assess for adverse events via self-report at all inperson visits. Participants will also be provided a study phone line to report an adverse event between visits. Any adverse events will be reported to the PI and then to the OUHSC IRB. The likelihood of an adverse (potential for nicotine overdose) event is low (< 1% in studies in our laboratory), and mild (nausea, headache), and will be handled quickly (i.e., advice to participants to reduce or stop tobacco use).

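### Visit 1's ad libitum session depends on cigarettes the participant brings, with only a floor of two and no count or run-out flag described, so the secondary puff, time and CO measures may be censored, with unknown size and direction of bias.

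*Combined protocol and SAP*

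**What the plan says.** The section on Laboratory Visit/Session 1 describes a "60-minute ad libitum smoking session" of the usual cigarette. The cigarettes are the participant's own, "which they will be instructed to bring with them to the first study visit", and the scheduling reminder sets the quantity: "they will be reminded to bring at least two of their cigarettes to the first study visit". Protection Against Risks confirms that usual-brand cigarettes are the "own brand provided by the participant"; the study supplies only the experimental brand.

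The Phase 1 overview requires at least 12 hours of abstinence, partly because it "produces optimal levels of smoking motivation that are sensitive to the experimental manipulations". At Visit 1, "smoking exposure (CO boost), and behavior (topography: number of puffs, total time smoked) will be measured".

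In the Phase 1/Aim 1 analyses, CO boost and puff topography ("number of menthol versus non-menthol cigarette puffs consumed, number of minutes smoked, interval between puffs") are secondary. The primary absolute reinforcing value (ARV) rests on ratings: "ARV of menthol cigarettes will be operationalized as between subject differences in subjective ratings of menthol vs non-menthol cigarettes". The candidate covariates are cigarettes per day, nicotine dependence, race/ethnicity, gender and age of onset. Supply is not among them. The Visit 1 section also allows the session to be done remotely.

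**The concern.** An ad libitum measure is informative because the participant decides when to stop. Here two people with the same wish to smoke can record different intakes because one carried two cigarettes and the other a pack. Puffs, minutes smoked and CO boost accumulate over the session, so running out truncates them. The topography device records the puffs taken, but not whether the participant stopped by choice or had none left. Unless supply is noted at the time, that cannot be recovered later.

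Visit 1 is also the only session with free intake. Visit 2 limits each experimental cigarette to 3 to 5 puffs, and Visit 3 allows at most 10 earned puffs. At stake is the menthol versus non-menthol comparison on these secondary measures, and whether a null or positive result on them can be read as reflecting behaviour rather than supply.

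**Working it through.** **Inputs from the documents.** 125 menthol and 125 non-menthol smokers (Study Objective); floor of two cigarettes, own supply, 60 minutes (Visit 1 section). The documents give no effect size, SD, power or session intake, so there is no plan figure to reproduce. Everything below is illustration under stated assumptions.

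**1. Structure.** Let W be the intake a person wants and S the intake their supply allows. The session records min(W, S). When W exceeds S, the record is a lower bound on W, that is, right-censored.

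**2. Reference effect.** Assume two-sided alpha 0.05 and 80% power. The detectable standardised difference is (1.960 + 0.842) × √(2/125) = 2.802 × 0.1265 = 0.354.

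**3. Same cap in both groups.** Assume W is N(0,1) for non-menthol and N(0.354,1) for menthol smokers. Let q be the share of non-menthol smokers who want more than two cigarettes allow, so the cap is c = Φ⁻¹(1 − q). The figures come from 1,000,000 simulated draws per group, with power from the resulting difference and SD at 125 per group.

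| q | All bring exactly two: difference (loss) | Power | Half bring exactly two: difference | Power |
|---|---|---|---|---|
| 1% | 0.349 (1%) | 80% | – | – |
| 10% | 0.307 (13%) | 78% | 0.330 | 79% |
| 30% | 0.226 (36%) | 73% | 0.290 | 75% |
| 50% | 0.152 (57%) | 63% | 0.254 | 67% |

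The loss is 1 − difference/0.354. Closed-form check at q = 10%, c = 1.282, using E[min(W,c)] = μΦ(c−μ) − φ(c−μ) + c[1 − Φ(c−μ)]:
- Menthol: 0.354 × 0.823 − 0.2595 + 1.282 × 0.177 = 0.259.
- Non-menthol: 0 − 0.1754 + 1.282 × 0.10 = −0.047.
- Difference: 0.306, in agreement with the simulation.

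Power falls less than the raw difference because the cap also reduces the SD (to 0.884 at q = 10%).

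**4. Supply that differs by group (q = 30%).**
- 25% of menthol and 75% of non-menthol smokers bring only two: the difference grows from 0.354 to 0.418.
- The reverse split: it falls to 0.162, with power 32%.
- No true difference, with the first split: a spurious 0.095 appears. A test would favour menthol about 13% of the time, against a nominal 2.5%.

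**5. A different demand model.** Let wanted cigarettes be whole numbers, 1 + Poisson(m − 1). Capped at two, the mean is 2 − exp(−(m − 1)). For m = 1.6 versus 1.9 the capped means are 1.451 and 1.593, a difference of 0.142 against a true 0.30. The loss is 1 − 0.142/0.30 = 53% if all bring two, and half of that, 26%, if half do. Power falls from about 78% to 61% and 70% respectively. For 1.4 versus 1.65 and 1.8 versus 2.1, the losses with all capped are 41% and 61%.

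**6. How many might want more than two.** If demand were Poisson, 8% would at mean 1, 19% at mean 1.5 and 32% at mean 2. The documents do not say which mean is realistic.

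**7. Dropping run-out sessions.** In the step 5 model with everyone bringing two, anyone wanting two or more uses the whole supply. Excluding them leaves only people who smoked one cigarette, and the group difference is exactly zero.

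**The case against.** The strongest reply is that the problem has not been shown to occur. The instruction sets a minimum, not a ration, and nothing in the documents shows that anyone brings only two or wants a third. Some-day smokers are eligible, and many may want one cigarette in an hour. This stands: run-out is a possibility, not a finding.

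A reader might infer that the group difference must shrink. The documents do not support that. It follows only if menthol demand is higher and supply limits both groups alike; step 4 shows that unequal supply can move the difference either way.

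A reader might also take the 41% to 61% losses in step 5 as the expected damage. They depend on counting whole cigarettes, so that a cap at two leaves a one-or-two outcome. Cigarettes smoked is not a listed outcome; puffs, minutes and CO boost also vary within a cigarette. Continuous demand gives much milder results when few are capped.

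A third inference would be that ARV itself is compromised. Its primary definition is subjective ratings, which supply does not directly cap, and the same holds for inter-puff interval. Remote sessions may escape the limit, since a reminder to bring cigarettes does not clearly apply at home.

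Finally, silence is not proof. Session forms are not among the documents, so the most that can be said is that no recording of supply is described. What survives is that, on the plan as written, a chosen stop and a forced stop cannot be told apart.

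**Conclusion.** The point holds in a limited form. Own supply with a floor of two, neither standardised nor described as recorded, may right-censor number of puffs, minutes smoked and CO boost at Visit 1. Under continuous demand and equal supply the effect is small if about 10% or fewer of the reference group want more than they brought (at most about 13% of the difference and 2 points of power), and material at 30% or more. Those figures rest on an assumed effect of 0.354 SD, normal demand and two-sided alpha 0.05. The whole-cigarette model gives larger losses, and the documents cannot decide between the two. Direction is unknown unless the number brought is known to be similar in the two groups. The documents do not support saying that sessions are capped at two, that the difference necessarily shrinks, or that the primary ARV outcome is affected. The importance is minor and confidence in any practical effect is low; the reason to act is that the remedy is cheap and the information cannot be recovered afterwards.

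**What to change.** Replace the floor of two with one common instruction, the same for both groups, under which supply is not expected to end the session. Log the number of cigarettes brought and the number left, for in-person and remote sessions alike, and flag each session in which supply ran out. Report the frequency of the flag by menthol preference. As a sensitivity analysis, treat puffs, minutes smoked and CO boost from flagged sessions as right-censored, for example by censored regression, and set the result beside the planned analysis. Do not exclude flagged sessions, because exclusion selects on the outcome (step 7).

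The cost is a sentence in the scheduling script, two logged counts with the flag derived from them, and one extra secondary sensitivity analysis. No visit or measurement is added. If the flag is rare, the log itself shows that the measures are sound.
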